8.3.3. Physical Examinations

Brief physical examinations will include examination of the heart, lungs, abdomen, and visual pelvic examination. In addition, any organ system in which a previous abnormality was noted at Baseline or a subject has a complaint or AE will be examined.

8.3.4. *Electrocardiograms*

A 12-lead ECG will be performed in the supine position at the Screening visit using an ECG machine that automatically calculates the heart rate and measures PR, QRS, QT, and QTc intervals. ECGs will be read by trained personnel at the study site or appropriate delegates who are medically qualified.

8.3.5. *Post-Void Residual Volume*

The volume of urine that remains in the bladder after voiding (PVR) is an objective measurement that may serve as a proxy for impaired ability to void. The physician should assess subjects with an increase in PVR volume to determine whether an AE should be reported. (Refer to [Section 8.4.6](#) for additional information on reporting AEs of urinary retention associated with increased PVR.)

The PVR assessment will be performed via ultrasound (eg, bladder scanner) at the visits indicated in the Schedule of Assessments ([Section 1.3](#) and [Section 1.4](#)). All efforts should be made to ensure the same device and operator are used for all PVR volume measurements for individual subjects.

8.3.6. *Clinical Safety Laboratory Assessments*

All protocol-required laboratory assessments must be conducted in accordance with the laboratory manual and the Schedule of Assessments. See [Section 10.2](#) for the list of clinical laboratory tests to be performed and the Schedule of Assessments for the timing and frequency. Repeat or unscheduled samples may be taken for safety reasons or for technical issues with the samples.

The clinical significance of test results will be evaluated as follows:

- At Screening (and at other eligibility assessment timepoints as specified in [Section 5.1](#) and [Section 5.2](#)), the investigator or physician subinvestigator will assess the clinical significance of any values outside the reference ranges provided by the laboratory, and subjects with abnormalities judged to be clinically significant will be excluded from the study.

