 - For subjects with systolic blood pressure \geq 140 mmHg **OR** diastolic blood pressure \geq 90 mmHg at **baseline** (Visit 3):
An increase, compared to baseline (Visit 3) at **2 consecutive visits**, in the average of 3 systolic blood pressures by \geq 20 mmHg **or** 3 diastolic blood pressures by \geq 10 mmHg
 - Initiation or increase in dose of medication for treatment of hypertension in any subject

Note 1: The onset date for an AESI hypertension is the first of the dates when the event meets any of the above criteria.

Note 2: An *AE of “increased blood pressure”* should be recorded if, in the investigator’s opinion, an elevated blood pressure measurement is clinically significant but does not fulfill the above definition for hypertension.

- Adverse events consistent with **orthostatic hypotension** as confirmed by orthostatic vital signs
- **Elevated serum aspartate aminotransferase (AST) or alanine aminotransferase (ALT)** lab value requiring that study drug be temporarily withheld or permanently discontinued (see [Sections 8.4.6.1](#) and [8.4.6.2](#)). To date, no concern regarding drug-induced liver toxicity has been identified; however, the Sponsor is monitoring laboratory data for a potential safety signal, consistent with Food and Drug Administration guidance [[FDA Guidance, 2009](#)].
- **Neoplasms**

Serious AESIs and elevated liver enzymes or bilirubin requiring withholding of study drug (see [Section 8.4.6.1](#)) must be reported within 24 hours of the study site personnel's knowledge of the event by marking the appropriate box on the AE eCRF and assigning the most appropriate category. Additional information should be provided as directed in the eCRF Completion Guidelines. AESIs that also meet the definition of an SAE must be reported as an SAE, as described in [Section 8.4.4](#). Nonserious AESIs should be reported within 72 hours of the site personnel's knowledge, using the AE eCRF.

8.4.6.1. Criteria for Temporary Withholding of Study Treatment in Association with Liver Test Abnormalities

Elevated liver enzymes or bilirubin sufficient to require withholding study medication must be reported **within 24 hours of the study site personnel's knowledge of the event** using AESI specific eCRFs/forms/worksheets provided for the study.

Hepatic enzymes will be monitored in accordance with FDA drug-induced liver injury guidelines [[FDA, 2009](#)].

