If **any** of the following liver test abnormalities develop, study drug should be withheld immediately with appropriate clinical follow-up (including repeat laboratory tests, until a subject's laboratory profile has returned to normal/baseline status), and the event reported as an SAE:

- ALT or AST $> 8 \times$ upper limit of normal (ULN)
- ALT or AST $> 5 \times$ ULN and persists for more than 2 weeks
- ALT or AST $> 3 \times$ ULN and total bilirubin $> 2 \times$ ULN or international normalized ratio (INR) > 1.5
- ALT or AST $> 3 \times$ ULN with appearance of fatigue, nausea, vomiting, right upper quadrant pain or tenderness, fever, rash and/or eosinophilia ($> 5\%$)

Rechallenge may be considered if an alternative cause for the abnormal liver tests (ALT, AST, total bilirubin) is discovered and the laboratory abnormalities resolve to normal or baseline values. The investigator and Sponsor's designated Medical Monitor must discuss and agree with any decision to rechallenge.

Rechallenge should not occur when the etiology of the liver test abnormalities is considered possibly drug-induced.

8.4.6.2. Criteria for Permanent Discontinuation of Study Treatment in Association with Liver Test Abnormalities

Study treatment should be discontinued permanently if **all** of the following 4 criteria are met (ie, potential severe drug-induced liver injury/Hy's law case):

- Total bilirubin increases to $> 2 \times$ ULN or INR > 1.5 **and**
- AST or ALT increases to $\geq 3 \times$ ULN **and**
- Alkaline phosphatase value does not reach $2 \times$ ULN **and**

- No alternative cause explains the combination of the above laboratory abnormalities; important alternative causes include, but are not limited to the following:
 - Hepatobiliary tract disease
 - Viral hepatitis (eg, hepatitis A/B/C/D/E, Epstein-Barr virus)
 - Exposure to hepatotoxic agents/drugs or hepatotoxins, including herbal and dietary supplements, plants, and mushrooms
 - Alcoholic hepatitis
 - Non-alcoholic steatohepatitis
 - Autoimmune hepatitis

If an alternative cause for hepatotoxicity is identified, then it should be determined (based on the severity of the hepatotoxicity or event) whether study drug should be withheld or permanently discontinued as appropriate for the safety of the subject, following consultation with the Sponsor's designated Medical Monitor.

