10.2. Appendix 2: Clinical Laboratory Tests

The tests detailed in [Table 4](#) will be performed by the central laboratory chosen by the Sponsor. Subjects do not need to fast prior to laboratory testing. A sample for urinalysis (including microscopy for RBCs, WBCs, epithelial cells, and bacteria) and urine culture will be sent to the central laboratory only if the urine dipstick tests positive for the presence of leukocytes, nitrites, or blood cells. If a subject reports symptoms suggestive of a urinary tract infection at any visit, a urine dipstick should be performed as needed, and a sample will be sent out for urinalysis and culture, and sensitivity testing.

Table 4 Clinical Laboratory Tests

Hematology	Chemistry	Urinalysis ^a	Other
Hematocrit	Albumin	Blood	PSA ^d
Hemoglobin	Alkaline phosphatase	Glucose	Coagulation INR/PT/APTT ^e
Platelet count	ALT	Protein	
WBC (total and differential)	AST	Specific gravity	
RBC	Bicarbonate	Microscopic exam (RBCs, WBCs, epithelial cells, and bacteria)	
	Calcium	pH	
	Chloride	Color	
	Creatinine ^b		
	Glucose (fasting or non-fasting)		
	Potassium		
	Sodium		
	Total bilirubin		
	Direct bilirubin ^c		
	Blood urea nitrogen		
	Total cholesterol		

ALT = alanine aminotransferase; APTT = activated partial thromboplastin time; AST = aspartate aminotransferase; eGFR = estimated glomerular filtration rate; INR = international normalized ratio; PSA = prostate-specific antigen; PT = prothrombin time; RBC = red blood cell count; WBC = white blood cell count

^a A sample for urinalysis and urine culture/sensitivity will be sent to the central laboratory only if the urine dipstick performed at the site is positive for the presence of leukocytes, nitrites, or blood cells.

^b eGFR will be calculated and reported by the central lab.

^c If total bilirubin is elevated above the upper limit of normal.

^d PSA performed by central laboratory at Screening.

^e Only upon request from Principal Investigator (if ALT, AST and bilirubin are increased).

10.3. Appendix 3: Adverse Events: Definitions and Procedures for Recording, Evaluating, Follow-up, and Reporting

Definition of an AE

AE Definition

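### The liver rules let INR > 1.5 stand in for raised bilirubin, but the laboratory table names no trigger for INR where it could decide them

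*Protocol*

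**What the plan says.** **The rules.** Protocol Section 8.4.6.1 lists four liver criteria. Any one of them calls for immediate withholding of study drug and reporting as an SAE. One is ALT or AST > 3 x ULN together with total bilirubin > 2 x "ULN or international normalized ratio (INR) > 1.5". Section 8.4.6.2 sets four conditions for permanent discontinuation, all of which must hold. The first is total bilirubin > 2 x "ULN or INR > 1.5". The others are AST or ALT >= 3 x ULN, alkaline phosphatase not reaching 2 x ULN, and no alternative cause.

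**The test.** Section 10.2 states that the Table 4 tests "will be performed by the central laboratory chosen by the Sponsor". INR, PT and APTT appear there under a footnote: "Only upon request from Principal Investigator (if ALT, AST and bilirubin are increased"). The same table handles direct bilirubin differently. It is run "If total bilirubin is elevated above the upper limit of normal", a trigger that depends on a laboratory value and needs no request.

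**Related text.** Section 8.4.6.1 also says "Hepatic enzymes will be monitored in accordance with FDA drug-induced liver injury guidelines". Section 8.3.6 says "All protocol-required laboratory assessments must be conducted in accordance with the laboratory manual and the Schedule of Assessments", and adds that "Repeat or unscheduled samples may be taken for safety reasons or for technical issues with the samples".

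**The concern.** In both rules INR is an alternative to bilirubin, so it adds information only when bilirubin has not already met its own threshold. The footnote makes raised bilirubin part of the condition for requesting INR. It also differs from the rules in two other ways:

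- It asks for ALT and AST to be increased, where the rules ask for ALT or AST.
- It leaves the test to the investigator's choice, where the rules direct an action.

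A site that follows the footnote as written could have a man with ALT at 4 x ULN, normal bilirubin and an INR above 1.5, and never learn the INR. The withholding criterion would be met but not known. The SAE report that follows from it would not be triggered, nor would assessment for permanent discontinuation. The repeat laboratory tests in 8.4.6.1 do not solve this, because they follow once a criterion has been recognised and do not name INR.

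**Working it through.** The plan gives no figure to reproduce, so the check sets the rule beside the footnote and counts logical combinations.

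**Inputs.** The bilirubin-or-INR criterion is from 8.4.6.1; 8.4.6.2 has the same structure with >= 3 x ULN. Availability of INR is from Table 4, footnote e.

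**Step 1: where INR can decide.** Put ALT and AST each at one of three levels (not above ULN; above ULN up to 3 x; above 3 x). Put bilirubin at one of three levels (not above ULN; above ULN up to 2 x; above 2 x).

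- Enzyme pairs with ALT or AST above 3 x ULN: 9 - 4 = 5.
- With bilirubin above 2 x ULN (5 combinations), the criterion is already met and INR is redundant.
- With bilirubin not above 2 x ULN, INR decides: 5 x 2 = 10 combinations.

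**Step 2: what footnote e gives in those 10.** The footnote does not define increased, so three readings are shown.

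| Reading of the footnote | INR may be requested | INR is triggered by a value or schedule |
|---|---|---|
| All three tests above ULN | 3 of 10 | 0 of 10 |
| Bilirubin above the rule's own 2 x ULN | 0 of 10 | 0 of 10 |
| Parenthesis only illustrates when a request is expected | 10 of 10 | 0 of 10 |

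In the first row, the 3 are the enzyme pairs with both ALT and AST above ULN, with bilirubin above ULN up to 2 x. The other 7 comprise the 5 with normal bilirubin and 2 with one enzyme normal. The last column is the result that does not depend on the reading. These are combinations, not patient frequencies.

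**Step 3: how far other criteria cover the same men.** Section 8.4.6.1 also withholds at ALT or AST > 8 x ULN, at > 5 x ULN persisting more than 2 weeks, and at > 3 x ULN with listed symptoms or eosinophilia. For withholding, that leaves men above 3 x ULN who have none of these features, bilirubin not above 2 x ULN, and INR > 1.5. Exclusion criterion 30 keeps out men with ALT or AST > 2 x ULN at entry. The other withholding criteria do not replace INR in 8.4.6.2, but 8.4.6.1 says a man already withheld should not be rechallenged if the cause is possibly the drug.

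**Step 4: cost scale.** The documents give no rate of ALT or AST >= 3 x ULN. Assuming 0.1% to 1% of 1088 men: 0.001 x 1088 = 1.1 and 0.01 x 1088 = 10.9, or about 1 to 11 men.

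**The case against.** The strongest reply is that nobody depends on footnote e alone. Section 8.3.6 allows unscheduled samples, says clinically significant values should be repeated, and provides for recording local results that change management. Section 8.4.3 obliges the investigator to arrange further tests when medically indicated or when the sponsor asks. Section 8.3 sends immediate safety concerns to the Medical Monitor. Section 7.1 lets the investigator stop drug for abnormal liver function in the subject's best interest, with or without an INR. Section 8.4.6 reports no liver concern to date, and Section 2.3.1 cites more than 2300 subjects exposed. All of this stands and is why the point is minor. None of these provisions names INR or ties it to a transaminase value, so they reduce the gap without closing it.

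Two stronger readings are tempting, and the documents do not support them:

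- A reader might infer that INR cannot be obtained when bilirubin is normal. The footnote governs central testing only and may be illustrative; other routes exist.
- A reader might infer that nothing in the trial's procedures calls for INR. The liver-injury guideline and the laboratory manual are invoked but are not available here. The supportable statement is that the visible protocol text names no trigger.

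A further objection concerns the remedy. Neither the exclusion criteria nor Appendix 6 bars anticoagulants, and no baseline INR is scheduled. A reflex INR could exceed 1.5 because of anticoagulation. Section 8.4.6.1, unlike 8.4.6.2, has no exemption for an alternative cause, so withholding and an SAE report would follow. This stands, and the fix has to deal with it.

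**Conclusion.** The inconsistency is real: two stated rules rely on a test whose own footnote does not call for it where it would decide the rule. Its practical size is small. It reaches asymptomatic men with ALT or AST at or above about 3 x ULN, bilirubin not above 2 x ULN, and no other criterion met. The number of decisions that would change cannot be derived from the documents.

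A reader might take the intervals between scheduled on-treatment laboratory visits (Days 29, 85 and 169, so 56 and 84 days) as the delay caused by this gap. They are not. They describe the chemistry schedule, would be the same after the fix, and are shortened by repeats of significant values. Nor does a missing INR mean that a man stays on drug, given the discretion in Section 7.1.

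The conclusion rests on the protocol text alone and would fall away if the laboratory manual already makes INR reflex on transaminases. It is a minor subject-safety point, worth correcting because the correction is cheap. Sample size, power and the efficacy analyses are untouched.

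**What to change.** 1. Reword Table 4, footnote e along these lines: INR is obtained whenever ALT or AST is >= 3 x ULN, regardless of bilirubin, at the repeat or an unscheduled draw; PT and APTT remain on request. This takes the value-triggered form already used for direct bilirubin.
2. Add to Section 8.4.6.1 that an INR > 1.5 explained by anticoagulant therapy does not by itself meet the criterion and is to be discussed with the Medical Monitor.

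No numerical threshold changes, and the alternative-cause condition in 8.4.6.2 stays as it is.

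**Cost.** One footnote and one sentence, plus one INR sample for each man reaching ALT or AST >= 3 x ULN (about 1 to 11 men under the assumed rates), possibly at an extra attendance because INR is not part of the routine panel. There may also be an occasional additional withholding and SAE report, which the second change limits but does not remove.

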10.4. Appendix 4: Abbreviations

Term	Description
5-ARI	5 α -reductase inhibitors
AE	adverse event
AESI	Adverse Events of Special Interest
ALT	alanine aminotransferase
APR	abdominoperineal resection
AR	adrenergic receptor
AST	aspartate aminotransferase
β 3-AR	beta-3 adrenergic receptor
BPH	benign prostatic hypertrophy
cAMP	cyclic adenosine monophosphate
CFB	change from baseline
CFR	Code of Federal Regulations
CFU	colony-forming unit
CIC	clean intermittent catheterization
CIOMS	Council for International Organizations of Medical Sciences
CONSORT	Consolidated Standards of Reporting Trials
CRF	case report form
CT	computerized tomography
DSMB	Data Safety Monitoring Board
ECG	Electrocardiogram
eCRF	electronic case report form
ED	erectile dysfunction
eGFR	estimated glomerular filtration rate
FAS	full analysis set
FAS-I	full analysis set for incontinence
FDA	(United States) Food and Drug Administration
GCP	good clinical practice
HRQL	health-related quality of life
ICF	informed consent form
ICH	International Council on Harmonisation of Technical Requirements for Registration of Pharmaceuticals for Human Use

Term	Description
ICS	International Continence Society
IDC	involuntary detrusor contraction
IEC	independent ethics committee
[REDACTED]	[REDACTED]
INR	international normalized ratio
IPSS	International Prostate Symptom Score
IRB	institutional review board
IWRS	interactive web response system
LAR	low anterior resection
LF	long form
LUTS	lower urinary tract symptoms
MCC	maximum cystometric capacity
MedDRA	Medical Dictionary for Regulatory Activities
MMRM	mixed model for repeated measure
MRI	magnetic resonance imaging
OAB	overactive bladder
[REDACTED]	[REDACTED]
P _{det} @1st IDC	maximum detrusor pressure during the first involuntary detrusor contraction
P _{det} @Max Storage	maximum detrusor pressure during the storage phase
P _{det} @Q _{Max}	Detrusor pressure at peak flow rate
PGI	Patient Global Impression
PRO	patient-reported outcome
PSA	prostate-specific antigen
PT	preferred term
PTNS	percutaneous tibial nerve stimulation
PVR	post-void residual
QD	once daily
Q _{max}	maximum urinary flow; peak flow rate during voiding
QTc	corrected QT
RBC	red blood cell
REB	research ethics board
REML	restricted (or residual) maximum likelihood
SAE	serious adverse event

Term	Description
SAF	Safety Analysis Set
SAP	statistical analysis plan
SNS	sacral neurostimulation
SOC	System Organ Class
SUSAR	suspected unexpected serious adverse reaction
TEAE	treatment-emergent adverse event
TESAE	treatment-emergent serious adverse event
ULN	upper limit of normal
Urovant	Urovant Sciences GmbH
US	United States
UTI	urinary tract infection
Vol@1 st IDC	volume at first involuntary detrusor contraction
VV	voided volume
WBC	white blood cell
WHO-DDE	World Health Organization Drug Dictionary Enhanced

10.5. Appendix 5: Study Tabular Summary

Parameter Group	Parameter	Value
Trial information	Trial Title	A Phase 3 Double-Blind, Randomized, Placebo-Controlled, Multi-Center Study to Evaluate the Efficacy, Safety and Tolerability of Vibegron in Men with Overactive Bladder (OAB) Symptoms on Pharmacological Therapy for Benign Prostatic Hyperplasia (BPH)
	Clinical Study Sponsor	Urovant Sciences, GmbH
	Trial Phase Classification	Phase 3
	Trial Indication	OAB Symptoms in Men with BPH
	Trial Indication Type	Treatment
	Trial Type	Randomized, controlled, double-blind
	Trial Length	Up to 25 weeks
	Planned Country of Investigational Sites	North America and Europe
	Planned Number of Subjects	1088 enrolled; 924 evaluable
	FDA-Regulated Device Study	No
Subject information	FDA-Regulated Drug Study	Yes
	Pediatric Study	No
	Diagnosis Group	OAB Symptoms with BPH
	Healthy Subject Indicator	No
	Planned Minimum Age of Subjects	45
	Planned Maximum Age of Subjects	None
	Sex of Subjects	Male
	Stable Disease Minimum Duration	3 months

Parameter Group	Parameter	Value
Treatments	Investigational Therapy or Treatment	vibegron
	Drug Type	drug
	Pharmacological Class of Invest. Therapy	beta-3 adrenergic receptor agonist
	Dose per Administration	75
	Dose Units	mg
	Dosing Frequency	Once daily
	Route of Administration	Oral
	Current Therapy or Treatment	Pharmacotherapy for BPH: alpha blocker monotherapy or alpha blocker + 5 ARI
	Added on to Existing Treatments	Subjects not receiving current treatments for OAB symptoms
	Control Type	Placebo
	Comparative Treatment Name	--
Trial design	Study Type	Randomized, controlled, double-blind
	Drug Model	Parallel
	Planned Number of Arms	2
	Trial is Randomized	Yes
	Randomization Quotient	1:1
	Trial Blinding Schema	Double blind
	Stratification Factor	Baseline average micturition episodes per day (≤ 12 vs > 12), alpha blocker use with or without 5-ARI (yes or no), and urinary incontinence (yes or no)
	Adaptive Design	No

BPH = benign prostatic hypertrophy; FDA = Food and Drug Administration; OAB = overactive bladder

10.6. Appendix 6: Prohibited Medications and Non-Drug Therapies

The following medications are prohibited, as outlined in [Section 6.5.1](#).

Prohibited Medications Class	Examples	Washout Period/Comments
Anticholinergics	darifenacin, fesoterodine, hyoscyamine, oxybutynin, propantheline, solifenacin, tolterodine, and trospium	Subject must discontinue use at least 28 days prior to beginning completion of the Screening Bladder Diary and remain off this therapy during the study. If an anticholinergic/ antimuscarinic is used in an inhaler on a PRN/ as needed basis for the treatment of chronic obstructive pulmonary disease, it will be permitted.
Smooth muscle relaxants	flavoxate, dicyclomine, propiverine	Subject must discontinue use at least 28 days prior to beginning completion of the Screening Bladder Diary and remain off this therapy during the study
Beta-2 adrenergic agonists used for the treatment of stress urinary incontinence	clenbuterol	Subject must discontinue use at least 28 days prior to beginning completion of the Screening Bladder Diary and remain off this therapy during the study
Systemic beta-2 adrenergic agonist	terbutaline	No washout period; subject must remain off this therapy during the study
Antidiuretic hormones	desmopressin	Subject must discontinue use at least 28 days prior to beginning completion of the Screening Bladder Diary and remain off this therapy during the study
Beta-3 adrenergic agonists	mirabegron	Subject must discontinue use at least 28 days prior to beginning completion of the Screening Bladder Diary and remain off this therapy during the study
New start of BPH medications	Alpha-Blockers, eg, alfuzosin, doxazosin, silodosin, tamsulosin, and terazosin 5-ARI, eg, alfuzosin, dutasteride, and finasteride PDE5 inhibitors, eg, tadalafil	Subject must not start new use of these therapies during the study.
Intradetrusor or intraprostatic botulinum toxins	intradetrusor injection of botulinum toxin or intraprostatic injections	Subject must not have received an injection within 6 months prior to the Screening Visit and must not receive this therapy during the study
Any herbal medications to treat OAB symptoms, lower urinary tract symptoms of BPH or erectile dysfunction		Subject must not have received the herbal medications within 28 days prior to the Screening Visit and must not receive them during the study.
Diuretics		Subject must not start new diuretics during the study.
Percutaneous tibial nerve stimulation (PTNS)		Subject must not start new PTNS or related therapies during the study.

